14.3 Vital Signs and Physical Examination

Vital signs variables include systolic blood pressure, diastolic blood pressure, heart rate, respiration rate, and temperature. Vital signs will be summarized descriptively by visit. Physical examinations will include assessments of general appearance; head, eyes, ears, nose, and throat; the cardiovascular, dermatologic, lymphatic, respiratory, gastrointestinal, genitourinary, musculoskeletal, and neurologic systems. Physical examination results (normal or abnormal) will be summarized descriptively by visit.

14.4 Electrocardiogram, Chest X-Ray and Liver Ultrasound

Electrocardiogram (ECG), chest X-ray and liver ultrasound are performed at the Screening visit with additional evaluations to be performed if clinically indicated during the study. Test results (normal, abnormal, or unknown) will be summarized or provided in data listings, as appropriate for the amount of data collected.

14.5 Viral Shedding

Viral shedding will be extensively studied at protocol specified time points including Baseline, BMN 270 infusion day, and post BMN 270 infusion until at least 3 consecutive negative results are obtained. Body fluids including blood, saliva, semen, urine and stool will be tested by polymerase chain reaction (PCR) at these time points. Testing of semen will continue at least through Week 12, even if 3 consecutive negative results have been recorded in that compartment prior to that time point. Subjects who have not had 3 consecutive negative semen samples by Week 52 should continue to have PCR testing in semen every 4 weeks (during Year 2) or every 6 weeks (during Years 3-5) until 3 consecutive negative samples are documented (or upon consultation between the Investigator and Medical Monitor).

The vector genomes tested in extracted body samples will be summarized by visit with descriptive statistics and in graphical format. In addition, the number (%) of patients with detectable vector genomes by visit and sample type, the duration of shedding by sample type, and the peak period(s) of shedding by sample type will be summarized. Values below the lower limit of quantitation (LLoQ) will be imputed as one half of the validated LLoQ of 50 vg/q PCR and back calculated to the theoretically corresponding genome amounts per standard unit of biospecimen.

15 IMMUNOGENICITY ASSESSMENT

Analysis of immunological parameters will be primarily descriptive. Assays to detect pre-existing immunogenicity specific for AAV5, including plasma derived inhibitors of transduction (transduction inhibition or TI) and total antibody (TAb) assays, will be tested at the Screening visit before BMN 270 infusion is given and at post-baseline visits according to the protocol's schedule of events. Test results (negative and positive with titer) will be summarized and provided in data listings, as appropriate for the amount of data collected.

Two assays are in place to determine immunogenicity to the human FVIII transgene product. The first is a total antibody (TAb) assay to detect binding antibodies in patient plasma directed against human FVIII and is reported as negative or positive with titer. The second is to evaluate NAb capable of interfering with FVIII activity (FVIII Inhibitors) and is determined using the Bethesda assay with Nijmegen modification. This assay is reported out in Bethesda Units (BU), with a value of <0.6 considered negative. Both assays will be performed on patient plasma samples obtained at the screening visit, and at post-baseline visits according to the protocol's schedule of events. Test results will be summarized and provided in data listings as appropriate for the amount of data collected. The associations between antibody responses and the occurrence of adverse events or other safety or efficacy endpoints, such as FVIII activity values and clinical chemistries, may be explored.

Cellular immunity in the form of cytotoxic T lymphocytes (CTL) will be evaluated by Interferon-gamma (IFN- γ) ELISpot assay of peripheral blood mononuclear cells (PBMC). PBMC will be stimulated with overlapping peptide pools derived from the AAV5 capsid protein or human FVIII protein sequences to evaluate IFN- γ secretion by CTL targeting both the AAV5 capsid and the FVIII transgene product. Cellular immunity will be evaluated at baseline and at post-infusion visits according to the protocol's schedule of events and is reported positive or negative by peptide pool stimulation and as spot forming units (SFU) per 10^6 PBMC. Test results will be summarized and data listings will be generated reporting positive or negative and the number of SFU 10^6 PBMC for each peptide pool and control stimulation for each patient at each study visit tested. Positive and negative results with the number of SFU per 10^6 PBMC will be evaluated for correlations with FVIII activity measures, changes in clinical chemistry or adverse events as appropriate for the data collected.

16 CLINICAL PHARMACOLOGY

Clinical pharmacology analyses will be specified in a separate clinical pharmacology analysis plan.

17 OTHER ANALYSIS

Study 270-303 was ongoing during the COVID-19 pandemic and remained ongoing despite the disruption that occurred. The study began enrollment after the pandemic was declared but had no impact on study sample size. However, pandemic might affect the study conduct.

Additional analyses will be conducted as appropriate to evaluate the impact of the COVID-19 pandemic on the study conduct and results, especially for the treatment effect as estimated in the trial. Summaries of study participation with missing visits, study disposition and protocol deviations due to COVID-19 pandemic will be provided.

19 SUMMARY OF CHANGES TO STUDY SAP

Version		Affected Section(s)	Summary of Revisions
Number	Date		
1.0	21FEB2023		Initial version
2.0	20APR2023	Section 5.1, Section 13	
 1. An mITT analysis population was defined to exclude subjects who were not on adequate prophylactic hemophilia therapy prior to BMN 270 infusion from the ITT population. The mITT population will be the primary analysis population for efficacy evaluations. 2. Clarification of baseline annualized utilization of exogenous FVIII replacement therapy and annualized number of bleeding episodes calculation time window.

20 APPENDICES
20.1 Analysis Visit Windows

Assessment	Derived Visit	Scheduled Visit Day^a	Window^b
FVIII activity assays	Baseline ^c	Day -7 – Day -1	≤ Day 1
	Weeks 1 - 4		Days [2, 32]
	Weeks 5 - 8		Days [33, 60]
	Weeks 9 - 12		Days [61, 88]
	Weeks 13 - 16		Days [89, 116]
	Weeks 17 - 20		Days [117, 144]
	Weeks 21 - 24		Days [145, 172]
	Weeks 23 – 26		Days [159, 186]
	Weeks 25 - 28		Days [173, 200]
	Weeks 29 - 32		Days [201, 228]
	Weeks 33 - 36		Days [229, 256]
	Weeks 37 - 40		Days [257, 284]
	Weeks 41 - 44		Days [285, 312]
	Weeks 45 - 48		Days [313, 340]
	Weeks 49 - 52		Days [341, 368]
	Week 56	Day 393	Days [369, 406]
	Week 60	Day 421	Days [407, 434]
	Week 64	Day 449	Days [435, 462]
	Week 68	Day 477	Days [463, 490]
	Week 72	Day 505	Days [491, 518]
	Week 76	Day 533	Days [519, 546]
	Week 80	Day 561	Days [547, 574]
	Week 84	Day 589	Days [575, 602]
	Week 88	Day 617	Days [603, 630]
	Week 92	Day 645	Days [631, 658]
	Week 96	Day 673	Days [659, 686]
	Week 100	Day 701	Days [687, 714]
	Week 104/EY	Day 729	Days [715, 743]
	Week 110	Day 771	Days [744, 792]
	Week 116	Day 813	Days [793, 834]
	Week 122	Day 855	Days [835, 876]
	Week 128	Day 897	Days [877, 918]
Week 134	Day 939	Days [919, 960]	
Week 140	Day 981	Days [961, 1002]	
Week 146	Day 1023	Days [1003, 1044]	

Assessment	Derived Visit	Scheduled Visit Day ^a	Window ^b
	Week 152	Day 1065	Days [1045, 1078]
	Week 156/EY	Day 1093	Days [1079, 1114]
	Week 162	Day 1135	Days [1115, 1156]
	Week 168	Day 1177	Days [1157, 1198]
	Week 174	Day 1219	Days [1199, 1240]
	Week 180	Day 1261	Days [1241, 1282]
	Week 186	Day 1303	Days [1283, 1324]
	Week 192	Day 1345	Days [1325, 1366]
	Week 198	Day 1387	Days [1367, 1408]
	Week 204	Day 1429	Days [1409, 1442]
	Week 208/EY	Day 1457	Days [1443, 1478]
	Week 214	Day 1499	Days [1479, 1520]
	Week 220	Day 1541	Days [1521, 1562]
	Week 226	Day 1583	Days [1563, 1604]
	Week 232	Day 1625	Days [1605, 1646]
	Week 238	Day 1667	Days [1647, 1688]
	Week 244	Day 1709	Days [1689, 1730]
	Week 250	Day 1751	Days [1731, 1772]
	Week 256	Day 1793	Days [1773, 1806]
	Week 260/EY	Day 1821	Days [1807, 1835]
Note: median or mean of the assessments within the above windows will be used for analysis.			
Annualized utilization (IU/kg) of exogenous FVIII replacement therapy, ABR	Baseline ^d		< Day 1
	Week 1 – FVIII Prophylaxis End		Days [1, the later date of Day 32 or the end of FVIII prophylaxis plus 2 days for products of standard half-life or plasma-derived and 4 days for products of extended half-life]
	Post FVIII Prophylaxis–Week 52		Days [the later date of Day 33 or the end of FVIII prophylaxis plus the washout period (3 days for products of standard half-life or plasma-derived and 5 days for products of extended half-life), 368]
	Post FVIII Prophylaxis Period		≥ the later date of Day 33 or the end of FVIII prophylaxis plus the washout period (3 days for products of standard half-life or plasma-derived and 5 days for products of extended half-life)

Assessment	Derived Visit	Scheduled Visit Day ^a	Window ^b
Note: all assessments within the above defined windows will be used to derive the corresponding endpoint.			
Number of FVIII infusions, Bleeds	Baseline ^d		< Day 1
	Week 1 – FVIII Prophylaxis End		Days [1, the later date of Day 32 or the end of FVIII prophylaxis plus 2 days for products of standard half-life or plasma-derived and 4 days for products of extended half-life]
	Post FVIII Prophylaxis–Week 52		Days [the later date of Day 33 or the end of FVIII prophylaxis plus the washout period (3 days for products of standard half-life or plasma-derived and 5 days for products of extended half-life), 368]
	Post FVIII Prophylaxis Period		≥ the later date of Day 33 or the end of FVIII prophylaxis plus the washout period (3 days for products of standard half-life or plasma-derived and 5 days for products of extended half-life)
Note: all assessments within the above defined windows will be used in analysis.			
PROs	Baseline ^c	Day -7 to Day -1	≤ Day 5
	Week 4	Day 29	Days [6, 57]
	Week 12	Day 85	Days [58, 134]
	Week 26	Day 183	Days [135, 274]
	Week 52	Day 365	Days [275, 448]
	Week 76	Day 533	Days [449, 630]
	Week 104/EY	Day 730	Days [631, 812]
	Week 128	Day 897	Days [813, 994]
	Week 156/EY	Day 1096	Days [995, 1176]
	Week 180	Day 1261	Days [1177, 1358]
	Week 208/EY	Day 1461	Days [1359, 1540]
	Week 232	Day 1625	Days [1541, 1722]
Week 260/EY	Day 1826	Days [1723, 1840]	
PBMC (ELISpot)	Baseline ^c	Day -7 to Day -1	≤ Day 1
	Week 2	Day 15	Days [2, 22]
	Week 4	Day 29	Days [23, 36]
	Week 6	Day 43	Days [37, 40]
	Week 8	Day 57	Days [41, 64]
	Week 10	Day 71	Days [65, 78]
	Week 12	Day 85	Days [79, 92]

Assessment	Derived Visit	Scheduled Visit Day^a	Window^b
	Week 14	Day 99	Days [93, 106]
	Week 16	Day 113	Days [107, 120]
	Week 18	Day 127	Days [121, 134]
	Week 20	Day 141	Days [135, 148]
	Week 22	Day 155	Days [149, 162]
	Week 24	Day 169	Days [163, 176]
	Week 26	Day 183	Days [177, 190]
	Week 28	Day 197	Days [191, 204]
	Week 30	Day 211	Days [205, 218]
	Week 32	Day 225	Days [219, 232]
	Week 34	Day 239	Days [233, 246]
	Week 36	Day 253	Days [247, 281]
	Week 44	Day 309	Days [282, 337]
	Week 52	Day 365	Days [338, 393]
	Week 64	Day 449	Days [408, 491]
	Week 76	Day 533	Days [492, 575]
	Week 88	Day 617	Days [576, 659]
	Week 100	Day 701	Days [660, 715]
	Week 104/EY	Day 730	Days [716, 772]
	Week 116	Day 814	Days [773, 856]
	Week 128	Day 898	Days [857, 940]
	Week 140	Day 982	Days [941, 1024]
	Week 152	Day 1066	Days [1025, 1080]
	Week 156/EY	Day 1096	Days [1081, 1138]
	Week 168	Day 1180	Days [1139, 1222]
	Week 180	Day 1264	Days [1223, 1306]
	Week 192	Day 1348	Days [1307, 1390]
	Week 204	Day 1432	Days [1391, 1446]
	Week 208/EY	Day 1461	Days [1447, 1503]
	Week 220	Day 1545	Days [1504, 1587]
	Week 232	Day 1629	Days [1588, 1671]
	Week 244	Day 1713	Days [1672, 1755]
	Week 256	Day 1797	Days [1756, 1811]
	Week 260/EY	Day 1826	Days [1812, 1840]
Liver tests, Vital signs, and other central lab tests	Baseline ^c	Day -1	≤ Day 1
	Week 1	Day 8	Days [2, 11]
	Week 2	Day 15	Days [12, 18]

Assessment	Derived Visit	Scheduled Visit Day^a	Window^b
	Week 3	Day 22	Days [19, 25]
	Week 4	Day 29	Days [26, 32]
	Week 5	Day 36	Days [33, 39]
	Week 6	Day 43	Days [40, 46]
	Week 7	Day 50	Days [47, 53]
	Week 8	Day 57	Days [54, 60]
	Week 9	Day 64	Days [61, 67]
	Week 10	Day 71	Days [68, 74]
	Week 11	Day 78	Days [75, 81]
	Week 12	Day 85	Days [82, 88]
	Week 13	Day 92	Days [89, 95]
	Week 14	Day 99	Days [96, 102]
	Week 15	Day 106	Days [103, 109]
	Week 16	Day 113	Days [110, 116]
	Week 17	Day 120	Days [117, 123]
	Week 18	Day 127	Days [124, 130]
	Week 19	Day 134	Days [131, 137]
	Week 20	Day 141	Days [138, 144]
	Week 21	Day 148	Days [145, 151]
	Week 22	Day 155	Days [152, 158]
	Week 23	Day 162	Days [159, 165]
	Week 24	Day 169	Days [166, 172]
	Week 25	Day 176	Days [173, 179]
	Week 26	Day 183	Days [180, 186]
	Week 27	Day 190	Days [187, 193]
	Week 28	Day 197	Days [194, 200]
	Week 29	Day 204	Days [201, 207]
	Week 30	Day 211	Days [208, 214]
	Week 31	Day 218	Days [215, 221]
	Week 32	Day 225	Days [222, 228]
	Week 33	Day 232	Days [229, 235]
	Week 34	Day 239	Days [236, 242]
	Week 35	Day 246	Days [243, 249]
	Week 36	Day 253	Days [250, 259]
	Week 38	Day 267	Days [260, 273]
	Week 40	Day 281	Days [274, 287]
	Week 42	Day 295	Days [288, 301]
	Week 44	Day 309	Days [302, 315]

Assessment	Derived Visit	Scheduled Visit Day^a	Window^b
	Week 46	Day 323	Days [316, 329]
	Week 48	Day 337	Days [330, 343]
	Week 50	Day 351	Days [344, 357]
	Week 52	Day 365	Days [358, 371]
	Week 56	Day 393	Days [372, 406]
	Week 60	Day 421	Days [407, 434]
	Week 64	Day 449	Days [435, 462]
	Week 68	Day 477	Days [463, 490]
	Week 72	Day 505	Days [491, 518]
	Week 76	Day 533	Days [519, 546]
	Week 80	Day 561	Days [547, 574]
	Week 84	Day 589	Days [575, 602]
	Week 88	Day 617	Days [603, 630]
	Week 92	Day 645	Days [631, 658]
	Week 96	Day 673	Days [659, 686]
	Week 100	Day 701	Days [687, 714]
	Week 104/EY	Day 730	Days [715, 743]
	Week 110	Day 772	Days [744, 792]
	Week 116	Day 814	Days [793, 835]
	Week 122	Day 856	Days [836, 877]
	Week 128	Day 898	Days [878, 919]
	Week 134	Day 940	Days [920, 961]
	Week 140	Day 982	Days [962, 1003]
	Week 146	Day 1024	Days [1004, 1045]
	Week 152	Day 1066	Days [1046, 1079]
	Week 156/EY	Day 1096	Days [1080, 1117]
	Week 162	Day 1138	Days [1118, 1159]
	Week 168	Day 1180	Days [1160, 1201]
	Week 174	Day 1222	Days [1202, 1243]
	Week 180	Day 1264	Days [1244, 1285]
	Week 186	Day 1306	Days [1286, 1327]
	Week 192	Day 1348	Days [1328, 1369]
	Week 198	Day 1390	Days [1370, 1411]
	Week 204	Day 1432	Days [1412, 1446]
	Week 208/EY	Day 1461	Days [1447, 1482]
	Week 214	Day 1503	Days [1483, 1524]
	Week 220	Day 1545	Days [1525, 1566]
	Week 226	Day 1587	Days [1567, 1608]

Assessment	Derived Visit	Scheduled Visit Day^a	Window^b
	Week 232	Day 1629	Days [1609, 1650]
	Week 238	Day 1671	Days [1651, 1692]
	Week 244	Day 1713	Days [1693, 1734]
	Week 250	Day 1755	Days [1735, 1776]
	Week 256	Day 1797	Days [1777, 1811]
	Week 260/EY	Day 1826	Days [1812, 1840]

^a Relative to the BMN 270 infusion day (Day 1)

^b Visit day is calculated as (visit date – date of infusion date + 1) if post infusion and (visit date – date of infusion date) if before infusion

^c Baseline visit value of FVIII activity is defined as the last available measurement prior to BMN 270 infusion excluding those within 72 hours after a FVIII infusion. Baseline visit value of other assessments is defined as the last available measurement prior to BMN 270 infusion.

^d Baseline value is derived from the period between 12 months prior to 270-303 screening and the BMN 270 infusion day.

EY: end of year visit.

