5.4 Visit Windows for Analysis

All efficacy and safety data will be summarized by week or by a duration of multiple weeks based on windows defined by study days, wherever applicable. An assessment for a subject will be classified according to the study day of the assessment and its corresponding analysis visit window (see Appendix 20.1 Analysis Visit Windows).

For the primary, secondary, and other efficacy endpoints, windows of multiple weeks are defined based on ranges of study days. Median, mean assessments, or annualized values from these windows may be used in efficacy analyses as deemed appropriate (see Section 13).

For the tertiary efficacy endpoints and the safety endpoints such as liver function tests and vital signs, the windows are designated for each scheduled week of visit and centered on a target day; for example, the target day for a Week 4 visit is Study Day 29. If there are two or more assessments within a designated window, the assessment that is closest to the target day will be used for analyses. If the two closest assessments to the target day are equidistant from the target day, then the mean of the two assessments will be used for analyses unless otherwise specified.

Appendix 20.1 Analysis Visit Windows lists the weeks assigned for the analyses of the clinical endpoint assessments and the corresponding range of treatment days (window) during which a visit may have occurred by analysis parameter.

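### The ELISpot Week 6 analysis window (Days 37 to 40) excludes its own scheduled Day 43, which falls in Week 8; separately, Days 394 to 407 belong to no ELISpot window

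*SAP*

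**What the plan says.** Section 5.4 of the SAP gives the assignment rule: "An assessment for a subject will be classified according to the study day of the assessment and its corresponding analysis visit window". For tertiary efficacy and safety endpoints, with liver tests and vital signs as examples, it adds that "the windows are designated for each scheduled week of visit and centered on a target day", and it settles multiple samples as follows: "If there are two or more assessments within a designated window, the assessment that is closest to the target day will be used for analyses".

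Appendix 20.1, PBMC (ELISpot), then lists a scheduled day and a window for each visit. The rows that matter here are:

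- "Week 4 Day 29 Days [23, 36"
- "Week 6 Day 43 Days [37, 40"
- "Week 8 Day 57 Days [41, 64"
- "Week 52 Day 365 Days [338, 393"
- "Week 64 Day 449 Days [408, 491"

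No row stands between Week 52 and Week 64. SAP versions 1.0 and 2.0 print the same rows.

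Section 15 says that ELISpot results will be summarized, listed for each patient and visit tested, and examined for correlation with FVIII activity, clinical chemistry or adverse events as the data allow.

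**The concern.** A visit window that leaves out its own scheduled day cannot do its job. The Week 6 window closes three days before Day 43, and Day 43 lies inside the Week 8 window. A programmer who follows the appendix literally will label a Day 43 sample as Week 8, and only samples taken 3 to 6 days before the scheduled day will count as Week 6.

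The Week 6 and Week 8 columns of the T-cell summary would then be wrong, and so would any correlation that pairs ELISpot with FVIII activity or laboratory values by visit. Week 6 falls inside the 19-week corticosteroid regimen (Day 1 to Day 133, Section 5.1) and soon after the four-week point following which FVIII prophylaxis is discontinued (Section 13.1), so a cellular immune response at that time is of interest.

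The uncovered span between Week 52 and Week 64 is a second, independent fault in the same table. It does not cause the Week 6 problem.

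**Working it through.** **Inputs.** Scheduled days and window bounds for all 40 post-baseline ELISpot rows come from Appendix 20.1; the classification rule comes from Section 5.4.

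**Check 1: is each target inside its own window?** For Week 6 the test is 37 ≤ 43 ≤ 40, which fails because 43 exceeds 40 by 3 days. The other 39 rows pass.

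**Check 2: width and position of the early rows** (width = upper − lower + 1).

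| Visit | Target | Window | Width | Days before / after target |
|---|---|---|---|---|
| Week 4 | 29 | 23 to 36 | 14 | −6 / +7 |
| Week 6 | 43 | 37 to 40 | 4 | −6 / −3 |
| Week 8 | 57 | 41 to 64 | 24 | −16 / +7 |
| Week 10 | 71 | 65 to 78 | 14 | −6 / +7 |

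Every other two-weekly row from Week 4 to Week 34 has the −6 / +7 shape. The two faulty rows together span 4 + 24 = 28 days, which is two 14-day windows, so only the boundary between them is misplaced.

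**Check 3: the rule the table follows.** Forty rows have 39 internal boundaries. Compare each upper bound with the midpoint of adjacent targets, rounded down:

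- Thirty-six agree exactly.
- Week 152 differs by one day (1080 against 1081).
- Week 6 is 10 days short: (43 + 57)/2 = 50 against 40.
- Week 52 is 14 days short: (365 + 449)/2 = 407 against 393.

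**Check 4: coverage.** Each lower bound should equal the previous upper bound plus 1. The only failure is Week 52 to Week 64, where 408 ≠ 393 + 1. Days 394 to 407 are uncovered: 407 − 394 + 1 = 14 days.

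**What happens to a Day 43 sample.** It falls in Days 41 to 64 and is therefore Week 8. This step needs no tie-break rule. For a subject sampled on Days 43 and 57, the distances from the Week 8 target are 14 and 0 days. If the closest-to-target rule applies, the Day 57 sample is kept and Week 6 is empty for that subject. If no sample nearer Day 57 exists, the Day 43 sample is reported as Week 8.

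**Dependence on visit tolerance.** The document does not give the permitted tolerance, so these are assumptions. At ±2 days (Days 41 to 45) every permitted day goes to Week 8. At ±3 days (Days 40 to 46) one of seven permitted days, Day 40, goes to Week 6. At ±7 days (Days 36 to 50) four of fifteen, Days 37 to 40, go to Week 6.

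**After correction.** With Week 6 at [37, 50], Week 8 at [51, 64] and Week 52 at [338, 407], every target lies in its own window and Days 2 to 1840 are covered without a gap.

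**The case against.** The Week 6 row cannot be defended as printed. A PDF reading error is unlikely, because Week 8 starts at Day 41, directly after Day 40, and both SAP versions agree. Nothing elsewhere in the SAP corrects it. The fair objections concern reach, and most of them stand.

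- A reader might infer that on-time Week 6 results are discarded. Section 5.4 states the closest-to-target rule for tertiary efficacy and safety endpoints without naming ELISpot, and immunogenicity has its own Section 15. Omission from the summary needs the rule to apply and a sample nearer Day 57 to exist. Even then, the listings keep the result.
- A reader might infer that all on-time samples, in up to 22 subjects, are misassigned and that the Week 6 column is nearly empty. Twenty-two is the number of subjects given in Section 4.2, not a count of Week 6 samples. With a tolerance of 3 days or more, some permitted samples would be classified correctly. Only the statement about the scheduled day itself is certain.
- Harm to the correlations is conditional. Section 15 does not say that they are matched by visit, and it calls the immunological analysis mainly descriptive.
- No ELISpot visit is scheduled within Days 394 to 407, so only late or unscheduled samples could fall there, and nothing shows that any did.
- The printed Week 52 window runs −27 / +28 around Day 365, the same shape as Week 44 around Day 309, so it could be called centred as Section 5.4 describes. Extending it to Day 407 makes it −27 / +42.

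The last objection does not rescue the gap. The table puts boundaries at midpoints even where that makes a window lopsided: Week 36, [247, 281] around Day 253, runs −6 / +28. Week 64 starting at Day 408 already implies that Week 52 ends at Day 407.

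**Conclusion.** The point holds as two separate table errors. First, the Week 6 window omits its scheduled Day 43 by three days, and under Section 5.4 a sample on that day becomes Week 8. Second, a 14-day span after Week 52 is unassigned.

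What follows for a Day 43 sample, omission or relabelling, depends on whether the closest-to-target rule covers ELISpot and on whether a sample nearer Day 57 exists. The number of samples affected by either fault is not known from the document.

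The consequence is limited to descriptive by-visit ELISpot summaries and any correlation done by visit. No primary or secondary efficacy analysis uses these windows. The errors should be corrected because code written to the text will reproduce them and the remedy is nearly free.

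**What to change.** In the PBMC (ELISpot) block of Appendix 20.1:

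- Week 6: Days [37, 50] in place of [37, 40].
- Week 8: Days [51, 64] in place of [41, 64].
- Week 52: Days [338, 407] in place of [338, 393]; Week 64 stays at [408, 491].

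Add a sentence to Section 5.4 or Section 15 saying whether the closest-to-target rule applies to ELISpot. The cost is three table rows, one sentence and the matching programming specification. No data collection changes, and ELISpot summaries already produced from the printed windows would need only a rerun.
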